## 7.7 Analysis visit definition

All efficacy variables and local tolerability variables will be summarized and analyzed by analysis visit. Analysis visit will be imputed according to the following algorithm to summarize the data by proper visit window interval. Study day is calculated as visit date minus the date of first application plus 1.

Table 4 Analysis Visit and Visit Window				
Analysis Visit	Analysis Visit Number in Derived Dataset	Target Study Day	Visit Window (Study Day)	
Baseline	1	1	[<=1]	
Week 1	2	8	[2-11]	
Week 2	3	15	[ 12 – 21 ]	
Week 4	4	29	[ 22 – 42 ]	
Week 8	5	57	[ 43 – 70 ]	
Week 12	6	85	>70	

If multiple measurements are taken in the same interval, the one closest to the target study day will be used for the analysis. If two measurements are taken with equal differences in timing compared with the target date, the nominal visit number (recorded on the CRF page) will used.

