	Screening Visit 1 (maximum 14 days+3 days prior to Baseline)	Baseline Visit	Week 1 Visit (±3 days)	Week 2 Visit (±3 days)	Week 4 Visit (±3 days)	Week 8 Visit (±3 days)	Week 12 Final/ET Visit ² (±5 days)
Skin Oiliness Scale (SOS) Questionnaire ¹¹		X					X
Self-assessment of facial acne improvement							X
Study drug(s) Dispensing (D) and Accountability (A)		D			D/A	D/A	A
Moisturizer/cleanser Dispensing (D)		D ¹⁰					
Dosing calendar Dispensed (D) returned and reviewed (RR)		D	RR	RR	RR	RR	RR
Exit Form ¹¹							X

- (1) Baseline visit must be performed maximum 14 days after Screening with a time window of +3 days. For women of childbearing potential, there must be at least 14 days between Screening and Baseline visits (for UPT reason). No re-screening will be allowed.
- (2) Week 12 procedures will be performed earlier in case of study discontinuation.
- (3) Confirm information at Baseline
- (4) For subject of childbearing potential only: Urine Pregnancy Tests will be performed at Screening, Baseline, Week 4, Week 8, Week 12. For pre-menstrual subjects re-confirm pre-menses status at every visit and in case of status change collect information on contraceptive method and perform a UPT. For the ones who begin menses after the Screening visit, urine pregnancy tests will be performed at the visit where there was a change in status and according to the schedule for females of childbearing potential (Baseline, Week 4, 8, 12/ET). Additional UPTs may be performed at the investigator's discretion.
- (5) Subjects 9 to 11 years of age who did not meet the criteria for moderate truncal acne at Baseline: PGA will be evaluated after baseline to allow the investigators to decide to start the treatment on the trunk if the subject develops truncal acne during the study whatever the PGA grade. Local tolerability will be assessed. The Lesion counts will not be evaluated.
- (6) Photos are not mandatory; subjects will be able to participate in the study even if they refuse to participate in photo procedures.
- (7) Collection of Adverse Events will begin after signing of the informed consent/assent form.
- (8) Medication that continues after Screening visit should be recorded on the Concomitant Medication page of the eCRF. Medical or surgical procedures occurring after Screening visit should be recorded on the Procedures page of the eCRF

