#### Sensitivity analyses

The above primary efficacy analysis will be repeated using the PP population using the primary multiple imputation method for missing values.

To assess the robustness of the primary efficacy result, the following sensitivity analyses will be conducted for each of the 3 co-primary efficacy endpoints (see Section 4.1) using the ITT population:

a. The same imputation method above will be repeated based on the Pattern-Mixture Model under the missing not at random (MNAR) assumption, by using the profiles from vehicle subjects with observed data to impute missing data.

b. LOCF (Last observation carry forward) approach

c. Subjects with missing IGA data at Week 12 will be considered as 'failures' for IGA success rate; and subjects with missing lesion counts data at Week 12 will be assigned the median change of lesion counts data from subjects who are 'failures' of IGA success within the same treatment group.

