#### 7.4.1.2 Analysis of the Secondary Efficacy Endpoint

The same statistical methods planned for the 3 co-primary efficacy endpoints will be used for the analyses of the 3 co-secondary efficacy endpoints using the overall ITTT population, with Multiple Imputation (MI) as primary imputation method for missing values (see Section 7.4.2.2).

If the superiority of CD5789 50  $\mu$ g/g to Vehicle is established for the primary efficacy endpoint, then CD5789 50  $\mu$ g/g will be declared superior to Vehicle in the secondary efficacy endpoint for the overall ITTT population if the two-sided p-value is statistically significant (< 0.05) for the difference between the 2 treatment groups in all 3 co-secondary efficacy endpoints.

As the testing of secondary efficacy endpoint is conditional on the success of primary efficacy endpoint, and all of the 3 co-secondary efficacy endpoints need statistical significance for the secondary efficacy endpoint to be successful, no Type I error adjustment is needed for the multiple comparisons of the 3 co-secondary efficacy endpoints.

The above secondary efficacy analysis will be repeated using the PPT population with the primary multiple imputation method for missing values.

Galderma R&D RD.06.SPR.18252 Page 17 of 25

The same sensitivity analysis methods to handle missing data planned for the primary efficacy endpoint will also be applied for the analyses of the secondary efficacy endpoint in the overall ITTT population.

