# 7.4.2.2 Handling of dropouts or missing data

The primary method of imputation for missing data will be MI (Multiple Imputation) using the Missing At Random (MAR) assumption.

Galderma R&D RD.06.SPR.18252 Page 18 of 25

For the primary MAR based multiple imputation, the MI procedure of the SAS system will be used to generate sets of data with missing values imputed from observed data. It is expected that the pattern of missing data will be monotonic, with slight deviations being corrected by the Markov Chain Monte Carlo (MCMC) method of the MI procedure.

Linear regression will be employed to model the missing lesion count data and a logistic regression model will be used for the ordinal IGA/PGA scores, with the following covariates included in the imputation model: treatment and non-missing data from earlier timepoints. IGA/PGA success will be calculated from the imputed IGA/PGA scores. The imputed datasets will be analyzed using the methodology described in Section 7.4.1.1 for changes in lesion counts, and IGA/PGA success. The results from the analysis of the multiple imputed datasets will be combined by the MIANALYZE procedure of the SAS system. The seed number to be used will be the protocol number (18252) and the number of imputation is planned to be 5.

For success rate, the final p-value from the CMH test stratified by analysis center on each multiply imputed dataset will be generated using the Schafer, J. L. Multiple Imputation Methodology. The final difference of success rate between treatment groups (CD5789 50  $\mu$ g/g – Vehicle) and the final 95% confidence interval of the difference from each multiply imputed dataset will be generated using the method by Bohdana Ratitch ed. al..

For changes in lesion counts, the final p-value, treatment difference (CD5789 50  $\mu$ g/g – Vehicle), and the 95% confidence interval of the treatment difference from the ANCOVA model on each multiply imputed dataset will be generated from the MIANALYZE procedure of SAS.

To assess the robustness of the primary efficacy results, the following sensitivity analyses will be also conducted:

a. The same imputation method above will be repeated based on the Pattern-Mixture Model under the missing not at random (MNAR) assumption, by using the profiles from vehicle subjects with observed data to impute missing data.

b. LOCF (Last observation carry forward) approach

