# 9 TABLE SHELLS AND REPORTING OUTPUT (GENERAL FEATURES)

The final list of tables and figures and their shells for the reporting of this study will be available in a separate document to be developed and will be finalized before database lock. Galderma R&D RD.06.SPR.18252 Page 24 of 25

Details of analysis specifications including but not limited to the SAS code will be documented on the table shells.

Galderma R&D RD.06.SPR.18252 Page 25 of 25

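### Does the closest-to-target rule in SAP 7.7 stop LOCF from carrying the last observation of subjects who withdraw early?

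*SAP*

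**What the plan says.** SAP 7.7 opens with "All efficacy variables and local tolerability variables will be summarized and analyzed by analysis visit". Table 4 then sets windows by study day: Week 1 is days 2-11 (target 8), Week 2 is 12-21 (target 15), Week 4 is 22-42 (target 29), Week 8 is 43-70 (target 57), and Week 12 is any day after 70 (target 85). For several readings in one window the rule is "If multiple measurements are taken in the same interval, the one closest to the target study day will be used for the analysis". For an exact tie, "the nominal visit number (recorded on the CRF page) will used".

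Footnote 2 to the Protocol's schedule of assessments says "Week 12 procedures will be performed earlier in case of study discontinuation". A withdrawing subject can thus have IGA, PGA and lesion counts on a day inside an earlier visit's window.

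The primary missing-data method is multiple imputation (MI) under missing at random (SAP 7.4.2.2). SAP 7.4.1.1 and 7.4.2.2 list a sensitivity analysis described only as "LOCF (Last observation carry forward) approach". SAP 7.4.1.2 extends it to the truncal endpoints: "The same sensitivity analysis methods to handle missing data planned for the primary efficacy endpoint will also be applied". The October 2017 clarification describes MI under MAR, under MNAR and with categorical predictors, and missing-as-failure (sections 6.2, 6.3, 6.4 and 6.6). It does not mention LOCF. SAP section 9 says "Details of analysis specifications including but not limited to the SAS code will be documented on the table shells".

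**The concern.** LOCF should carry the last reading. Under 7.7, taken literally, the last reading may be removed before LOCF is applied. Take a Week 4 visit on day 29 and an ET visit on day 38. Both fall in days 22-42, at 0 and 9 days from target, so day 29 is kept and day 38 is dropped. LOCF on windowed records would then carry day 29.

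This is the usual direction of the rule and not a rare corner. Whenever the scheduled visit took place on or after its target day, every later ET reading in that window loses. At stake is whether a named sensitivity analysis for the three co-primary and three co-secondary endpoints does what its name says, and whether two programmers would derive it alike from the same text.

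**Working it through.** **Inputs.** Table 4 windows and the selection rule (SAP 7.7); visit tolerance of ±3 days for Weeks 1 to 8 (Protocol, schedule of assessments); 504 evaluable and 600 randomized per arm, 16% drop-outs and non-evaluable subjects, planned differences of 3 inflammatory and 6 non-inflammatory lesions (SAP section 6).

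**The plan's own figure.** SAP 7.7 states no figure on this point. The attrition figure used below reproduces: 504 / (1 − 0.16) = 600 per arm, so the allowance is 0.16 × 1200 = 192 subjects.

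**Step 1: which ET days lose.** Take first application on the Baseline day, ET days 2 to 84 (83 days), and all four scheduled visits displaced from target by the same number of days.

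- On target (days 8, 15, 29, 57), the later days in the four windows number 3 + 6 + 13 + 13 = 35, and all are dropped: 35/83 = 42%.
- Three days late (11, 18, 32, 60): 0 + 3 + 10 + 10 = 23, all dropped: 23/83 = 28%.
- Three days early (5, 12, 26, 54): 6 + 9 + 16 + 16 = 47 later days. ET is strictly closer to target on 5 days per window (20) and tied on 1 per window (4). So 47 − 20 − 4 = 23 are dropped if a tied ET reading is kept, and 27 if it is not.
- For visits 1, 2 or 3 days early, the dropped share of later in-window days is 31-35 of 39 (79-90%), 27-31 of 43 (63-72%) and 23-27 of 47 (49-57%).

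The range is 23 to 35 of 83 days. Leaving out the four scheduled-visit days gives 35 of 79 (44%) on target.

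**Step 2: how much older the retained reading is.** On target, the summed lags are 6 + 21 + 91 + 91 = 209 days over 35 cases, a mean of 6.0. Across the displacements the mean runs from 5 to 11 days. The maximum is 70 − 54 = 16 days.

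**Step 3: how many subjects (illustration only).** The documents give neither ET timing nor ET attendance. Assume that all 192 withdraw, that ET days are uniform over 2-84, and that each subject attended the preceding scheduled visit. The count is 192 × attendance × (0.277 to 0.422):

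| ET attendance (assumed) | Subjects affected |
|---|---|
| 25% | 13-20 |
| 50% | 27-40 |
| 100% | 53-81 |

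**Step 4: effect on the LOCF estimate.** The affected share is 13.3/1200 = 0.011 to 81.0/1200 = 0.068. With equal shares in both arms, each 1 lesion by which the older reading shifts one arm more than the other moves the difference by 0.01 to 0.07 lesions. For IGA success, assume a 10-point difference between arms, among affected subjects, in the share whose success status changes. The movement is then 0.011 × 10 = 0.1 to 0.068 × 10 = 0.7 percentage points, against a planned 23 − 15 = 8.

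**Step 5: what does not move.** An ET reading up to day 70 is never a Week 12 value, whichever record its window keeps. Missing-as-failure, in which "subjects with missing lesion counts data at Week 12 will be assigned the median change of lesion counts data", is therefore the same either way. The primary MI may condition on the older reading, but it does so under one pre-specified rule for every subject. An ET reading alone in its window, or strictly closer to target than the scheduled visit, is kept. One after day 70 with no other reading there becomes the Week 12 value, and LOCF is not needed.

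**The case for a change.** The best case for acting is that the silence is real and stands out. The October 2017 clarification was written to supply analysis detail. It gives that detail for the other missing-data methods and omits LOCF. For laboratory values and vital signs (clarification 7.5 and 7.6) it does name the last post-baseline visit, so the sponsor could have done the same here. The opening sentence of 7.7 covers all efficacy variables and speaks of analysis as well as summary, so the windowed reading is a natural one. A robustness analysis should be fixed before unblinding, and settling the point would cost a sentence or two.

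What stands is the silence, and the possibility of two derivations. The rest is weaker:

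- The next sentence of 7.7 gives the purpose of the algorithm as summarizing by visit window, which supports confining the rule to by-visit data. The plain meaning of LOCF is the last observation.
- The tie rule is less open than it looks. The schedule has one column for the final and ET visit, so an ET reading plausibly carries the Week 12 number. A tie in an earlier window would then go to the scheduled visit. Ties affect one day per window, and only when that visit was early.
- A short insertion is not obviously an improvement. Telling LOCF to take the last post-baseline assessment by date, without more, could override the closest-to-target value for a subject with two readings after day 70. It would give no value to randomized subjects with no post-baseline assessment. It would also prefer a later reading that may be off treatment, since section 7.1 of the clarification describes visits after treatment end. That is a choice between defensible conventions and not the correction of an error.

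**Conclusion.** The conditional statement is correct: LOCF built on the windowed records would sometimes carry a reading that is not the last. No error in the plan is shown. This is missing detail of the kind an analyst fills sensibly from the name of the method or from the table shells, which are due before database lock and cannot be checked here.

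The size is small: 23 to 35 of 83 possible ET days, a retained reading at most 16 days older, and about 0.01 to 0.07 lesions per lesion of differential shift. The day counts rest on first application at Baseline and visits within 3 days of target. The subject counts, and the effect sizes derived from them, rest on unsourced ET timing and attendance and on treating the whole 16% allowance as withdrawals. Withdrawals that coincide with scheduled visits produce no displacement and would lower the counts. The lesion scale also assumes equal affected shares in both arms; with unequal shares, a shift common to both arms would move the difference too.

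LOCF stands beside the per-protocol, vehicle-based MNAR, missing-as-failure and categorical MI analyses, and it does not enter the success criterion. No bias in the primary result is shown, and no change to the plan follows.

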# 8 CHANGES FROM THE PROTOCOL ANALYSIS PLAN

Any change from the protocol will be justified and fully documented.

# 9 TABLE SHELLS AND REPORTING OUTPUT (GENERAL FEATURES)

The final list of tables and figures and their shells for the reporting of this study will be available in a separate document to be developed and will be finalized before database lock. Galderma R&D RD.06.SPR.18252 Page 24 of 25

Details of analysis specifications including but not limited to the SAS code will be documented on the table shells.

Galderma R&D RD.06.SPR.18252 Page 25 of 25

#### 1. Purpose

The purpose of this document is to give details and clarifications about the analysis as presented in the Statistical Analysis Plan dated October 5, 2015. Any changes from the planned analysis as described in that document are also detailed here, and any differences described here supersede the analysis as presented in the SAP.

#### 2. General Clarification and Considerations

#### 2.1. Decimal Precision

Unless otherwise noted, means and medians will be presented to one more decimal place than the source data; standard deviations will be presented to two more decimal places than the source data; minimums and maximums will be presented to the same number of decimal places as the source data, percentages will be presented to one decimal place; confidence intervals will be presented to two decimal places; and p-values will be presented to three decimal places.

#### 2.2. Missing Date Procedures

Adverse events with completely missing dates will be considered treatment-emergent. Medications with completely missing end dates will be considered concomitant. Adverse events and medications with partially missing start or end dates will be considered treatment-emergent and concomitant respectively unless the non-missing portion of the dates definitively proves otherwise.

For example, if a subject starts treatment on 10FEB2015, then adverse events with onset dates of FEB2015, 2015, or 05DEC would all be considered treatment-emergent, while onsets dates of 2014 or JAN2015 would not be considered treatment-emergent. Medications starting or ending in FEB2015 or 2015 would be considered concomitant, medications ending in JAN2015 or 2014 would not.

#### 2.3. Coding Versions

Adverse events, procedures, and non-drug therapies are coded using MedDRA 18.0. Medications and therapies are coded using WHO-DDE v2013 March.

#### 2.4. Subgroup Analysis

Subgroup analyses for IGA and PGA success rate at Week 12, absolute change from baseline for inflammatory and non-inflammatory lesion counts at Week 12 on the face and trunk, treatment-emergent adverse events by SOC and PT, and local tolerability parameters worsened from baseline on the face and trunk will include an analysis by:

- Age: 9-11 years, 12-17 years, and  $\geq 18$  years of age
- Gender: female and male
- Age and gender: female <25 years, male <25 years, female >=25 years, and male >=25 years
- Race: White, Black or African American, Asian, and Other
- Ethnicity: Hispanic or Latino and Not Hispanic or Latino
- Skin Phototype: I-III and IV-VI

In addition, a subgroup analysis for IGA and PGA success rate at Week 12, treatment-emergent adverse events by SOC and PT, and local tolerability parameters worsened from baseline on the face and trunk will be provided for the additional age categories of: <14 Years, 14-17 Years, and >=18 Years.

#### 2.5. Subpopulations

Three subpopulations of the ITT population will be studied using the primary and secondary efficacy analyses. Those populations are defined as:

- Subjects with at least 75% non-inflammatory baseline lesions. A subject's baseline total noninflammatory lesion count will be divided by their baseline total lesion count (inflammatory and non-inflammatory). If the result is greater than or equal to 0.75, they will be included in the subpopulation. Presence of nodules and/or cysts will not be included for the calculation of inflammatory lesion counts.
- Subjects with no prior use of topical or oral retinoids. Use of topical and oral retinoids are identified using the ATC4 codes of D10AD and D10BA from the concomitant medication dataset.
- Subjects with no prior use of medications for acne. Subjects with use of prior medication of acne are identified using the following indication terms from the concomitant medications dataset:
  - o ACNE
  - o ACNÉ
  - ACNE ULGARIS
  - ACNE CONGLOBATA
  - ACNE FACE WASH
  - ACNE FACE/CHEST/BACK
  - ACNE ON FACE
  - ACNE VULARIS
  - ACNE VULGARIS
  - ACNE VULGARIS AND PITYROSPORUM FOLLICULITIS
  - ACNE VULGARIS OF FACE
  - ACNE VUOLGARIS
  - ACNE WASH
  - AKNE VULGARIS
  - FACIAL ACNE
  - FACIAL ACNE VULGARIS

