9. The subject has clinically significant abnormal laboratory values according to the Investigator at Screening (to be checked prior to Baseline).
10. The subject has known or suspected allergies or sensitivities to any components of any of the study drugs (see Investigator's Brochure).
11. The subject is a female who is lactating.
12. The subject is a female who intends to conceive a child during the trial or within 1 month after the last study drug application.
13. The subject is currently participating in any other clinical trial of a drug or device OR past participation in any other clinical trial within the 30 days prior to the Baseline visit.
14. The subject was previously or is currently enrolled in the long term safety study RD.03.SPR.18250 conducted by Galderma.
15. The subject has received, applied, or ingested the following treatments within the specified time frame prior to the Baseline visit as defined in below:

Treatment restrictions

Topical treatment on the face and trunk:	
Antibiotics	2 weeks
Benzoyl peroxide	
Azelaic acid	
Zinc	
Corticosteroids	
Other topical treatments (including laser)	4 weeks
Retinoids	
Topical procedures on the face and trunk:	
Phototherapy devices for acne (e.g., ClearLight™)	1 week
Adhesive cleansing strips (e.g., Pond®, Biore®)	
Cosmetic procedures (i.e., facials, peeling, comedone extraction)	
Systemic treatment:	
Non-steroidal anti-inflammatory drugs ¹	2 weeks
Corticosteroids (except inhaled corticosteroids or intrathecal corticosteroids)	4 weeks
Antibiotics (except plain penicillin)	4 weeks
Oral retinoids	6 months
Immunomodulators, including biologics	6 months

Note:

1) During the study, the use of Non-steroidal Anti-Inflammatory Drugs (NSAIDs) is acceptable for up to 21 days (cumulative) of treatment; however, it should be avoided during the 1 week period prior to the final study assessment.

No time frame period is specified for Alpha-hydroxy acid products, medicated shaving creams, after-shaves, colognes, astringents, or preparations with alcohol, but their application is prohibited during the study.

16. The subject has been exposed to excessive ultraviolet (UV) radiation within one month prior to the Baseline visit or the subject is planning intense UV exposure during the study (i.e., occupational exposure to the sun, sunbathing, tanning salon use, phototherapy, etc.)

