#### 7.3 Medical history, previous and concomitant therapies/procedures

For statistical analysis purpose, previous therapies/procedures are defined as those ending at Baseline visit or before; and concomitant therapies/procedures are defined as those ongoing at the Baseline visit or starting after the Baseline visit.

Previous and concomitant therapies will be coded using WHODRUG dictionary). Previous and concomitant procedures will be coded using MedDRA dictionary.

A summary table will be provided for each of the following in the ITT population:

- 1. number and percentage of subjects who had previous therapies/medications by ATC text and WHO drug name
- 2. number and percentage of subjects who had concomitant therapies/medications by ATC text and WHO drug name
- 3. number and percentage of subjects who had previous procedures by System organ class and preferred term
- 4. number and percentage of subjects who had concomitant procedures by System organ class and preferred term

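### The two no-prior-use subpopulations are drawn from concomitant medication data with no date condition, so use begun after randomization can remove a subject

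*SAP*

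**What the plan says.** Addendum section 2.5 states: "Three subpopulations of the ITT population will be studied using the primary and secondary efficacy analyses". Two of the three are defined by history: no prior use of topical or oral retinoids, and no prior use of medication for acne.

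- **Retinoids.** Topical and oral retinoid use "are identified using the ATC4 codes of D10AD and D10BA from the concomitant medication dataset".
- **Acne medication.** "Subjects with use of prior medication of acne are identified using the following indication terms from the concomitant medications dataset". A list of verbatim terms follows.

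Neither bullet gives a start date, an end date or a look-back period, and neither names the previous-therapy records as a source.

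SAP section 7.3 separates the two kinds of record. On one side, "previous therapies/procedures are defined as those ending at Baseline visit or before"; on the other, "concomitant therapies/procedures are defined as those ongoing at the Baseline visit or starting after the Baseline visit". The protocol's schedule of assessments has its own row for previous therapies and procedures, and footnote 8 to that schedule says: "Medication that continues after Screening visit should be recorded on the Concomitant Medication page of the eCRF".

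**The concern.** A subgroup defined by treatment history should be fixed before randomization. Here the history is read from a dataset whose name, under the SAP's own definition, includes therapy begun on study. A subject who first used a retinoid at Week 6 would carry one of the listed codes and drop out of the group without prior use. Starting another acne product during the trial can depend on how well the assigned cream is working, so the exclusion can differ by arm and the comparison within the subgroup loses the protection of randomization.

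The second risk runs the other way. If the dataset holds only concomitant records, a subject who used a retinoid in the past and stopped in time to be eligible leaves no trace in it and is counted as never having used one. The results would then be reported under a label that does not describe the subjects.

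**Working it through.** **Plan figures.** This point rests on no figure in the plan. The illustrations borrow the SAP section 6 success rates of 23% and 15%. Those reproduce the stated sample size: 504 per arm for 90% power at two-sided 0.05 (pooled variance, no continuity correction), and 504 / 0.84 = 600.

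**1. Can post-randomization use remove a subject?** Put the two texts side by side. Addendum 2.5 searches the concomitant dataset by code or term. SAP 7.3 places therapies starting after Baseline among concomitant ones. Nothing in 2.5 filters them out. The plan also expects such records: SAP 5.5 lists interfering therapy during treatment as a potential major deviation, and addendum section 5 flags prohibited drugs on the concomitant medications listing. The answer is yes for retinoids. For acne medication the word prior appears in the identifying sentence, but no rule applies it.

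**2. Can prior users be missed?** This depends on what the dataset holds.

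- Exclusion criterion 15 applies if "The subject has received, applied, or ingested the following treatments within the specified time frame prior to the Baseline visit". The washout for topical retinoids reads as 4 weeks (the table is broken in the available text, so this is a reading) and for oral retinoids 6 months. Screening is at most 14 + 3 = 17 days before Baseline.
- Topical retinoids: 28 − 17 = 11, so an eligible user stopped at least 11 days before Screening. Oral retinoids stopped far earlier. Neither continues past Screening or is ongoing at Baseline.
- Acne drugs with a 2-week washout: 14 − 17 = −3, so one could continue up to 3 days past a Screening visit at day −17 and be entered on the concomitant page. The 11-day gap does not carry over to these drugs.

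So if the dataset holds only records that are concomitant under SAP 7.3, washed-out retinoid users are not found. If it combines previous and concomitant records, they can be.

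**3. Size of the first problem.** The documents give no on-study use rates, so these are assumptions. Suppose only IGA failures start such drugs, a fraction x of vehicle failures and y of active failures, and that the whole-trial rates apply. After removal, the vehicle rate is 0.15 / (1 − 0.85x) and the active rate is 0.23 / (1 − 0.77y).

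| x (vehicle) | y (active) | Vehicle | Active | Difference (points) |
|---|---|---|---|---|
| 0 | 0 | 15.0% | 23.0% | 8.0 |
| 2% | 1% | 15.3% | 23.2% | 7.9 |
| 5% | 2% | 15.7% | 23.4% | 7.7 |
| 10% | 5% | 16.4% | 23.9% | 7.5 |
| 10% | 2% | 16.4% | 23.4% | 7.0 |

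The direction follows from the assumption. With x = 2% and y = 5%, the rates are 15.26% and 23.92%, and the difference rises to 8.7 points.

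**4. Size of the second problem, if it occurs.** Prior-use rates are also not given. Let u be true prior use among 1200 subjects and m the share of prior users missed. The group has 1200(1 − u) + 1200um members, of whom 1200um are prior users.

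| u | Correct group size | Size if half missed (prior users in it) | Size if all missed (prior users in it) |
|---|---|---|---|
| 20% | 960 | 1080 (11%) | 1200 (20%) |
| 40% | 720 | 960 (25%) | 1200 (40%) |
| 60% | 480 | 840 (43%) | 1200 (60%) |

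**The case against.** The strongest reply is that the dataset is probably one combined file. Section 2.5 itself looks there for prior acne medication, so its authors seem to believe prior records are in it. The long list of misspelt indication terms looks like it was drawn from collected records, in a trial that requires washout. Addendum section 2.2 classifies medications as concomitant or not by date, which fits a mixed file. Footnote 8 instructs sites about one eCRF page; it does not say that the page takes nothing else, and it does not describe how the dataset is assembled. This stands. A reader might infer that the retinoid-naive group would contain nearly all prior retinoid users, but the documents do not support that as a finding. It holds only if the file is limited to concomitant records, and the wording of 2.5 points the other way.

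A second reply is that both subpopulations are named by the word prior, so a sensible programmer would apply a Baseline cut. That has some force for acne medication, where the identifying sentence repeats the word. It has less for retinoids, where the sentence covers any use. A combined file does not remove the need for a cut, because it would hold earlier and later records together.

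A third reply is that on-study use is restricted, so few subjects would be affected, and that no confirmatory test is involved. Both parts are fair and they limit the weight of the point.

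**Conclusion.** The point holds in a limited form. As written, and most clearly for retinoids, the rule can remove a subject for medication begun after randomization, whether or not the dataset also holds previous-therapy records. Missing washed-out retinoid users is a conditional second problem that depends on dataset contents the documents leave unstated.

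The effect is probably small. In the illustrations with more on-study use on vehicle, the 8.0-point difference falls to between 7.9 and 7.0 points; with the imbalance reversed it rises to 8.7. These figures assume the usage rates, assume that every user is a failure, and apply whole-trial success rates to a subgroup. Misclassification of prior users could be larger, but only under the less likely reading of the dataset.

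A reader might also infer that the efficacy conclusion is at risk because the primary and secondary analyses are repeated in these groups. It is not. SAP sections 7.4.1.2 and 7.4.2.5 confine the testing sequence to the co-primary endpoints and then the co-secondary endpoints, and these subpopulations lie outside it. What is at stake is whether the additional results mean what their label says.

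**What to change.** In addendum section 2.5, for both subpopulations:

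1. Identify prior use from previous-therapy and concomitant records together, keeping those with a start date before the first study drug application, or before the Baseline visit date for a randomized subject who was never dosed.
2. State that medication started on or after that date does not remove a subject.
3. Count a record with a missing or partial start date as prior unless the known part shows that it began on or after the first application. Addendum section 2.2 settles only whether such a record is concomitant.

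The cost is one or two sentences in the addendum and one date filter in the program. No new data are needed, provided the previous-therapy records are available with their dates, and the primary and secondary analyses do not change.
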